8.1 Definitions

Unanticipated Problems Involving Risk to Subjects or Others

Any incident, experience, or outcome that meets all of the following criteria:

- Unexpected in nature, severity, or frequency (i.e. not described in study-related documents such as the IRB-approved protocol or consent form, the investigators brochure, etc)
- Related or possibly related to participation in the research (i.e. possibly related means there is a reasonable possibility that the incident experience, or outcome may have been caused by the procedures involved in the research,
- Serious (as defined below) “Serious” is different than “severe” as reported in the CTC criteria that applies a grade to the AE.

Adverse Event

An **adverse event** (AE) is any symptom, sign, illness or experience that develops or worsens in severity during the course of the study. Intercurrent illnesses or injuries should be regarded as adverse events. Abnormal results of diagnostic procedures are considered to be adverse events if the abnormality:

- results in study withdrawal
- is associated with a serious adverse event
- is associated with clinical signs or symptoms
- leads to additional treatment or to further diagnostic tests
- is considered by the investigator to be of clinical significance

Serious Adverse Event

Adverse events are classified as serious or non-serious. A **serious adverse event** is any AE that is:

- fatal
- life-threatening
- requires or prolongs hospital stay
- results in persistent or significant disability or incapacity
- a congenital anomaly or birth defect
- an important medical event

Important medical events are those that may not be immediately life threatening, but are clearly of major clinical significance. They may jeopardize the subject, and may require intervention to prevent one of the other serious outcomes noted above. For example, drug overdose or abuse, a seizure that did not result in in-patient hospitalization, or intensive treatment of bronchospasm in an emergency department would typically be considered serious.

All adverse events that do not meet any of the criteria for serious should be regarded as **non-serious adverse events**.

Adverse Event Reporting Period

The study period during which adverse events will be reported is normally defined as the period from the initiation of any study procedures to the end of the study treatment follow-up. For this study, the study treatment follow-up is defined as 30 days following the last administration of study treatment.

Preexisting Condition

A preexisting condition is one that is present at the start of the study. A preexisting condition will be recorded as an adverse event if the frequency, intensity, or the character of the condition worsens during the study period.

General Physical Examination Findings

At screening, any clinically significant abnormality will be recorded as a preexisting condition. At the end of the study, any new clinically significant findings/abnormalities that meet the definition of an adverse event will also be recorded and documented as an adverse event.

Post-study Adverse Event

All unresolved adverse events will be followed by the investigator until the events are resolved, the subject is lost to follow-up, or the adverse event is otherwise explained. At the last scheduled visit, the investigator will instruct each subject to report any subsequent event(s) that the subject, or the subject's personal physician, believes might reasonably be related to participation in this study.

Abnormal Laboratory Values

A clinical laboratory abnormality should be documented as an adverse event if any one of the following conditions is met:

- The laboratory abnormality is not otherwise refuted by a repeat test to confirm the abnormality
- The abnormality suggests a disease and/or organ toxicity
- The abnormality is of a degree that requires active management; e.g. change of dose, discontinuation of the drug, more frequent follow-up assessments, further diagnostic investigation, etc.

Hospitalization, Prolonged Hospitalization or Surgery

Any adverse event that results in hospitalization or prolonged hospitalization will be documented and reported as a serious adverse event unless specifically instructed otherwise in this protocol. Any condition responsible for surgery will be documented as an adverse event if the condition meets the criteria for an adverse event.

Neither the condition, hospitalization, prolonged hospitalization, nor surgery are reported as an adverse event in the following circumstances:

- Hospitalization or prolonged hospitalization for diagnostic or elective surgical procedures for a preexisting condition. Surgery should **not** be reported as an outcome of an adverse event if the purpose of the surgery was elective or diagnostic and the outcome was uneventful.
- Hospitalization or prolonged hospitalization required to allow efficacy measurement for the study.
- Hospitalization or prolonged hospitalization for therapy of the target disease of the study, unless it is a worsening or increase in frequency of hospital admissions as judged by the clinical investigator.

COVID-19

Any participant that develops symptoms of COVID-19 including but not limited to: fever, cough, shortness of breath, nausea, abdominal pain, headache, loss of taste or smell, or has known contact with a COVID-19 positive carrier will be asked to contact their PCP, their local COVID-19 hotline and the study team immediately. All study procedures will be put on hold until the participant has received a negative test result or has quarantined for 14 days while monitoring their symptoms. If a participant is confirmed positive for COVID-19, the appropriate case report forms will be completed in accordance with CDC guidelines and UNC Policy.

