3.1 General Design

Overview. This is an observational, single-center study using tissue-selective estrogen complex (TSEC) to examine the role of frontostriatal hypoactivity in the pathophysiology of perimenopausal MDD. This study will include 6 study visits that will take place over the course of approximately 6 weeks. Out of those 6 visits, 2 of them will require subjects to come to UNC's campus for their MRI visits at BRIC, while the rest of the appointments will be done virtually through HIPAA compliant Zoom, Webex, or phone when zoom is not available. Five visits will require brief in-person contact for phlebotomy, these very brief points of contact will be performed outside the subject's home when possible (i.e. backyard, back porch, or screened porch). In the context of COVID-19, all participants and staff will complete the appropriate screening as recommended by UNC and BRIC policy prior to any in-person contact. During in person visits participants and the study team will be required to wear masks at all times and maintain 6 feet distance when possible to minimize the possibility of COVID-19 transmission. Perimenopausal MDD women will receive Duavee, a TSEC, for 3 weeks. FMRI sessions will occur at baseline and at the end of the third week of medication administration. The procedures that will take place are outlined in **Table 1** and detailed below.

Table 1. Study Procedures and Timeline

Study Visits	1	2	3	4	5	6
Maximum duration of in-person visit (hours)		1	2	0.15	0.15	2
Consent	X					
OBGYN Exam		X				
fMRI			X			X
PRT			X			X
Venipuncture		X	X	X	X	X
SCID	X					
SNAP	X		X	X	X	X
HAM-D	X		X	X	X	X
IDAS	X		X	X	X	X
GCS	X		X	X	X	X
PSQI			X			X
HHQ						X
THQ						X
Duavee Rx Provided			X	X	X	
Payment	\$100	\$30	\$150	\$35	\$35	\$150

Participants. Participants will include healthy, unmedicated perimenopausal women ages 44-55 with (n=20) current major depression.

Hormone Administration.

Prior to beginning medication, women will have a basic lab panel and serum pregnancy test, pelvic exam, breast exam, and PAP smear. Participants who can provide record of a pelvic exam and breast exam within the past year and normal pap results within the past three years will be permitted to decline the GYN exam. Women will be seen in the clinic each week during medication administration to assess blood levels of estradiol and mood symptoms.

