8.2 Recording of Adverse Events

At each contact with the subject, the investigator will seek information on adverse events by specific questioning and, as appropriate, by examination. Information on all adverse events will be recorded immediately in the source document, and also in the appropriate adverse event module of the case report form (CRF). All clearly related signs, symptoms, and abnormal diagnostic procedures results will be recorded in the source document, though will be grouped under one diagnosis.

All adverse events occurring during the study period will be recorded. The clinical course of each event will be followed until resolution, stabilization, or until it has been determined that the study treatment or participation is not the cause. Serious adverse events that are still ongoing at the end of the study period will be followed up to determine the final outcome. Any serious adverse event that occurs after the study

period and is considered to be possibly related to the study treatment or study participation will be recorded and reported immediately.

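### The plan records adverse events of any cause for 30 days after the last dose, but the reviewed visit tables end at about the last dose and the final-visit instruction asks for later events believed related

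*Combined protocol and SAP*

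**What the plan says.** **Reporting period.** Section 8.1 (Adverse Event Reporting Period) starts AE reporting at the first study procedure and closes it with follow-up, where "the study treatment follow-up is defined as 30 days following the last administration of study treatment".

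**What is recorded.** Section 8.2 states: "All adverse events occurring during the study period will be recorded". The definition in section 8.1 is not limited to related events: "Intercurrent illnesses or injuries should be regarded as adverse events".

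**How events are found.** Section 8.2: "At each contact with the subject, the investigator will seek information on adverse events by specific questioning".

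**Schedule.** Section 3.1: "This study will include 6 study visits that will take place over the course of approximately 6 weeks". On the scans, which Table 1 places at visits 3 and 6: "FMRI sessions will occur at baseline and at the end of the third week of medication administration". Table 1 and the Appendix A table both end at visit 6.

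**Instruction at the last scheduled visit.** Section 8.1 (Post-study Adverse Event) has the investigator tell each woman "to report any subsequent event(s) that the subject, or the subject's personal physician, believes might reasonably be related to participation in this study".

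**After the period closes.** Section 8.2 applies a relatedness test to a serious event that arises after the study "period and is considered to be possibly related to the study treatment or study participation will be recorded and reported immediately".

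**The concern.** The recording rule covers all causes for 30 days after the last dose. The only general instruction a woman receives for that time is framed around events thought related. Section 8.2 brings in relatedness only once the study period is over, and only for serious events. The visit 6 instruction brings it in about 30 days sooner, while the period is still open.

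At stake is whether the plan can deliver its own rule. An infection, an injury or a hospital admission that a woman regards as nothing to do with the study falls inside the AE period, but no one is scheduled to ask about it. For a serious event this also touches section 8.3.1, which wants SAEs of any type telephoned to the PI and IRB within 24 hours. The annual report in Appendix A (III.B) must list AEs and judge whether their rates fit pre-study assumptions, and that judgement is weaker if capture changes after visit 6.

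**Working it through.** The plan gives no figure to reproduce here. The check sets the provisions side by side and adds timeline arithmetic.

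**1. Is there a causality filter inside the period?** Sections 8.1 (definition) and 8.2 (recording) give none. The relatedness wording in section 8.2 concerns serious events after the period.

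**2. Where does visit 6 fall?** Treatment lasts 3 weeks = 21 days, and visit 6 is the scan at the end of the third week. Taking visit 6 to be on the last-dose day (an assumption):

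- Period closes on day 21 + 30 = 51, counted from the first dose.
- Time between visit 6 and closure: 51 − 21 = 30 days.
- If visit 6 may fall up to 3 days after or before the last dose (an assumed tolerance), this becomes 30 − 3 = 27 to 30 + 3 = 33 days.
- Share of the time from first dose to closure: 30 / 51 = 59%.
- Share of the whole period, if visits 1 to 6 take 6 × 7 = 42 days: 30 / (42 + 30) = 30 / 72 = 42%.

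These are shares of time, not of events.

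**3. Does any reviewed text imply a later contact?**

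- Section 3.1 counts six visits over about 42 days. First dose to closure alone takes 51 days, so that duration does not stretch to a day-30 contact.
- The visit payments in Table 1 are 100 + 30 + 150 + 35 + 35 + 150 = $500, which equals the total in section 12.3. No paid contact lies beyond visit 6.

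**4. What can still capture an event in those 30 days?**

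- AEs already open are followed until resolved or explained (section 8.1). This does not find new events.
- Women may report events believed related (section 8.1).
- COVID-type symptoms and exposures are to be reported to the study team (section 8.1), if that request still applies after visit 6.
- AE questions are asked at any contact that happens to occur (section 8.2), such as confirming that the payment card arrived (section 12.3) or the optional symptom review with the PI (Appendix A, Potential Benefits).
- Women who stop drug early are asked to keep completing self-report ratings (section 4.4.2). This does not apply to completers.

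None of these is a scheduled inquiry about new events of any cause.

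**The case against.** **The instruction sits under a post-study heading, so it may concern the time after day 30.** That reading would match section 8.2. But the instruction is given at the last scheduled visit and covers whatever follows. If it did apply only after day 30, the reviewed text would hold no general instruction for the 30 days, so the gap would remain.

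**A reader might infer that women are told not to report unrelated events, or that no later contact exists anywhere.** The documents support neither. Other reports are not barred. The flowchart (section 6), the monitoring plan (section 10.1), the full consent form (section 11) and the text between sections 5.3 and 5.5 were not available. Any of them could state a later contact or a broader instruction. This stands, and the conclusion is conditional on it.

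**Not every document requires unrelated SAEs to be expedited.** Section 8.3 lists related, unexpected events, and Appendix A (II.B) sets a one-week limit for serious events that are also unanticipated problems. But section 8.3 describes its list as a minimum, and section 8.3.1 still names SAEs of any type. The differing timelines are a separate matter.

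**A reader might infer that mood worsening after stopping the drug would be missed.** The support for this is thin. A woman treated for depression with a hormone who worsens on stopping it is likely to think the two related, so the present instruction would reach her. Appendix A gives women the option to continue hormones, and the consent text quoted in section 3.1 offers outpatient care for depression resulting directly from participation. The withdrawal evidence in sections 1.1 and 1.2 concerns estradiol, and section 1.1 says this product's effect on depression is untested.

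**Passive capture suits a short, low-risk course.** Appendix A rates the risk as a minor increase over minimal, and section 3.4 lists no primary safety endpoint. This stands: passive capture is a defensible choice. What does not fit is pairing it with an all-cause recording rule.

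**Conclusion.** The mismatch is real but minor. On the text reviewed, completers have about 30 days inside the AE period with no scheduled inquiry, under an instruction narrower than the recording rule. New events thought unrelated would then come to light only through unprompted reports or incidental contact. This applies to up to 20 women.

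The conclusion assumes that visit 6 falls at about the last dose and that no unavailable attachment adds a contact or widens the instruction. No count or proportion of missed events can be given, because the documents contain no event rate for this interval; the 59% and 42% above must not be read that way. The analyses for Aims 1 and 2 use data up to visit 6 and are not affected.

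**What to change.** **Main change.** In section 8.1, reword the visit 6 instruction. For 30 days after the last dose, each woman reports any new or worsening symptom or illness, including low mood or suicidal thoughts, whatever she thinks caused it. After that she reports events thought related. This brings the instruction into line with section 8.2. It costs one sentence, plus a matching line in the consent form if that form repeats the present wording.

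**Optional addition.** Existing staff make one brief phone or video AE inquiry at about 30 days after the last dose, in a format section 3.1 already uses, with a column added to both visit tables. The cost is up to 20 × 1 = 20 short calls. The call relies on recall of up to 30 days, so it supplements the reworded instruction and does not replace it. A depression rating with the section 4.4.1 cut-off of 20 is not needed, since that rule discontinues women who are still on study.

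If an attachment already provides a later contact, a cross-reference from section 8.1 and the reworded instruction are enough.

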lingering in enclosed spaces from asymptomatic carriers. However this risk should not be any greater than being in an essential public setting such as a grocery store. If a participant or a member of the study team has had direct or even secondary contact with any suspected or confirmed cases of COVID, the study team will reschedule any upcoming visits until the case is confirmed negative or to quarantine for at least 14 days and monitor symptoms. If a participant or study team member experiences any symptoms of COVID-19 including but not limited to: cough, fever, chest pain, trouble breathing, loss of smell or taste, nausea, abdominal pain, vomiting, etc. participants will be asked to notify the study team immediately, contact their Primary Care Provider and their local COVID-19 hotline to get tested for COVID-19.

2 Study Objectives

The long-term research objectives are to 1) advance our understanding of the effects of ovarian hormones on the female brain and how these effects contribute to the triggering of and susceptibility to mood disorders; and 2) to identify neural and endocrine markers of depression risk, thereby improving our ability to prevent affective illness in women. Our central hypothesis is that the neural reward system is hypoactive in PM-MDD, and the antidepressant effects of a three-week TSEC intervention will be associated with increased activity in the neural reward system, assessed using functional magnetic resonance imaging (fMRI).

Aim 1: Determine the extent to which TSEC reduces anhedonia and other depressive symptoms in PM-MDD. Anhedonia and other depressive symptoms will be assessed at baseline and following 3 weeks of TSEC administration.

Aim 2 (Exploratory): Quantify the effect of TSEC on the neural reward system in PM-MDD. We will use fMRI at baseline and following TSEC treatment in PM-MDD to probe frontostriatal reward circuitry. We also will compare the effects of TSEC and ERT in PM-MDD.

Null hypothesis (H_0): TSEC has no salutary effect on depression.

Alternative hypothesis (H_1): TSEC reduces depression as evidenced by 1) a statistically significant decrease in average MASQ Anhedonia scale score following 3 weeks of treatment, and 2) a clinically significant increase of 1 SD in MASQ Anhedonia scale score.

We will test this hypothesis using a paired t-test of MASQ Anhedonia scores at visit 1 (pre-treatment) and visit 6 (post-treatment).

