4.4 Early Withdrawal of Subjects

4.4.1 When and How to Withdraw Subjects

Participants with significant clinical or laboratory abnormalities will be discontinued from the study prior to estrogen administration.

Adverse mood symptoms will be monitored by administering the Hamilton Rating Scale for Depression (HRSD) at each study visit. If suicidal thoughts or severe mood symptoms are **observed at any period in the protocol, then the HRSD will be administered on consecutive days for three days. Anyone scoring > 20 on the HRSD or expressing concerns about their ability to continue in the study, will be considered to have severe mood symptoms and be discontinued from the protocol.** In the event of the occurrence of severe mood symptoms, the protocol will be terminated. Should this step prove to be unsuccessful, conventional medication will be prescribed as needed. Further, although we do not anticipate severe adverse reactions, we have arranged for inpatient hospital admission in the Psychiatry Department if symptoms are otherwise unmanageable.

Any patient experiencing clinically significant side effects such as nausea, hypertension, vomiting or extreme fluid retention from the medication will have the dose titrated to achieve relief of the symptoms. If adequate relief cannot be achieved in this manner, drug treatment will be discontinued.

The determination of when and how to withdrawal subjects will be overseen by the study's principal investigator, co-investigators, and research coordinators and will be reported to the UNC Biomedical IRB.

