5.7 Packaging

The UNC Investigational Drug Service will receive the active drug from their Pharmacy storeroom. All the Duavee tablets will be provided to participants at study visit 3, in its original blister packaging. Duavee tablets are to be taken once daily. The remaining tablets will be returned to the study team at the conclusion of each subject's participation in the study, and returned to IDS for appropriate disposal.

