We do not expect any adverse side effects associated with the hormonal manipulations outlined in this protocol for the following reasons: We will be administering estrogen paired with selective estrogen receptor modulators (SERMs). SERMs are synthetic non-steroidal agents that have estrogen agonist and antagonist effects in different tissues, to block the negative effects of estrogen on non-target tissues, including the reproductive organs and cardiovascular system, while allowing estrogen to exert effects on target tissues like the brain, and thus decreasing risk for side effects.

Duavée: Nausea is the most common side effect of TSEC administration. At conventional replacement doses, higher than those employed in this protocol, this complaint seldom interferes with eating, and no weight loss has been reported. Abdominal pain, hot flashes, breast engorgement, endometrial hyperplasia and bleeding are also common side effects of TSEC administration. Pre-existing fibroid tumors of the uterus may enlarge under the effects of TSECs; however, at the dosage and for the duration of estrogen administration in this protocol this risk is small.

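### The COVID-19 hold stops all study procedures, including the mood and adverse-event checks already done remotely, and leaves dosing during a hold and the timing of visit 6 undefined

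*Combined protocol and SAP*

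**What the plan says.** The COVID-19 paragraph of section 8.1 applies to a participant who has had known contact with a positive carrier or who develops any one of an open-ended list of symptoms: "fever, cough, shortness of breath, nausea, abdominal pain, headache, loss of taste or smell". She is asked to contact the study team immediately. The rule then reads: "All study procedures will be put on hold until the participant has received a negative test result or has quarantined for 14 days".

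Section 1.5 has a parallel rule with a different trigger and length. After direct or secondary contact with a suspected or confirmed case, "the study team will reschedule any upcoming visits until the case is confirmed negative or to quarantine for at least 14 days". For symptoms, section 1.5 asks only for notification and testing.

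Other sections bear on the same point:
- **Drug effects.** Appendix A (Duavee Side Effects) says "Nausea is the most common side effect of TSEC administration", and "Abdominal pain, hot flashes, breast engorgement, endometrial hyperplasia and bleeding are also common side effects of TSEC administration".
- **Mood safety.** Section 4.4.1 monitors adverse mood symptoms with the "Hamilton Rating Scale for Depression (HRSD) at each study visit". HAM-D is a row of Table 1, the table of study procedures, and the HRSD is described again in section 6 (Study Procedures).
- **Remote contact.** In section 3.1, two visits are MRI visits on campus, "while the rest of the appointments will be done virtually through HIPAA compliant Zoom, Webex, or phone when zoom is not available".
- **Tablets.** Section 5.7 says "All the Duavee tablets will be provided to participants at study visit 3", and section 6 agrees. The schedules in Table 1 and Appendix A mark Duavee as provided at visits 3, 4 and 5.
- **Timing and analysis.** Section 3.1 puts the second scan at the end of the third week of medication. Section 7.2 compares visit 1 with visit 6. Section 7.3 analyses protocol-compliant participants only.

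**The concern.** A woman who reports nausea or abdominal pain after starting the drug meets a COVID-19 trigger and may also be having a drug reaction. Section 4.4.1 treats nausea as a possible side effect that needs a clinical response, while section 8.1 pauses every procedure. Nothing says how the two rules interact.

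Holding the remote assessments brings no infection control, because they involve no contact. What they do provide is the scheduled, researcher-rated mood check in unmedicated women with current major depression. The section 4.4.1 escalation, repeat HRSD on three consecutive days, is itself a study procedure and would fall under the same literal hold.

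The second stake is the endpoint. Visit 6 supplies the post-treatment MASQ-AD score and the second scan. No section gives a window for that visit, a dosing rule during a hold, or a rule for analysing a visit 6 that was delayed.

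**Working it through.** The plan gives no figure of its own on this point, so the check is a comparison of text and a day count.

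**1. Overlap of triggers and drug effects.** Section 8.1 names seven symptoms. Appendix A calls two of them (nausea, abdominal pain) common drug effects. Four (fever, cough, shortness of breath, loss of taste or smell) are not listed there. The seventh, headache, has only a partial link: section 1.4 says estrogens may precipitate migraine, then calls such risks negligible at this dose and duration.

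**2. What needs to be in person.** At visits 4 and 5, Table 1 caps in-person time at 0.15 hours (0.15 × 60 = 9 minutes), which fits the brief phlebotomy contact in section 3.1. The HRSD, self-report scales and adverse-event questions at those visits need no contact. Visit 6 is an MRI visit, but its self-report scales are collected by Qualtrics or on paper (section 6), so they too can be separated from the scan.

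**3. Day count.** Assumptions:
- Visit 3 is day 0, and visits 4, 5 and 6 fall on days 7, 14 and 21. The plan says weekly visits and three weeks of drug, but gives no day numbers.
- The hold starts on day s and lasts the full 14 days, so procedures resume on day s + 14. There is no early negative test.
- A visit on day d is covered if s ≤ d < s + 14. The earliest visit 6 is day max(21, s + 14).

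| Hold starts (day) | Visits covered | Earliest visit 6 |
|---|---|---|
| 1 to 7 | days 7 and 14 | day 21 |
| 8 to 14 | days 14 and 21 | days 22 to 28 |
| 15 to 21 | day 21 | days 29 to 35 |

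Any start on days 1 to 14 therefore covers 2 of the 3 on-treatment HRSD contacts. For a start on days 1 to 7, the first on-drug HRSD moves from day 7 to days 15 to 21 (1 + 14 = 15; 7 + 14 = 21).

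**4. What a late visit 6 measures.** For starts on days 8 to 21:
- If tablets end on day 21, visit 6 comes 22 − 21 = 1 to 35 − 21 = 14 days after the last one.
- If tablets continue without a break, exposure at visit 6 is 22 to 35 days instead of 21.
- If dosing is paused, exposure is interrupted, and the timing depends on whether the missed days are made up.

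The documents state neither the dosing rule nor the number of tablets dispensed, so none of these can be selected.

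**5. If such women are excluded (illustration only).** Section 7.1 does not state alpha. With a two-sided 0.05 paired t-test and a standardized effect of 0.7, power is 84.4% with 20 women, 79.9% with 18 and 74.5% with 16. The number of holds is unknown, so this shows only that a few exclusions matter at this sample size.

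**The case against.** The strongest reply is that adverse-event surveillance does not stop, and that stands. A reader might infer from the hold that adverse-event recording is suspended, but the documents do not support this. Section 8.1 has the symptomatic participant contact the team at once, and section 8.2 requires adverse-event questioning at each contact, so the trigger itself prompts a check. Sections 8.1 and 8.2 require every event to be recorded and followed, and section II.B of Appendix A requires a report with an attribution score. None of these has a COVID-19 exemption. Recording nausea or abdominal pain as a possible drug event is therefore already required. What lapses on a literal reading is the scheduled, visit-based questioning and the HRSD. A call made by the participant does not replace a scheduled rating.

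Other objections also narrow the point:
- Section 1.5 does not repeat the symptom trigger. Its rescheduling follows contact, and its 14 days is a minimum, whereas the section 8.1 hold ends at 14 days or earlier on a negative test.
- That the whole tablet supply is at home during a hold rests on sections 5.7 and 6, which both visit schedules contradict.
- The day counts are a worst case. A prompt negative test shortens all of them, and the documents give no test turnaround or hold frequency.

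None of this supplies an exception for remote assessments or a rule for a late visit 6.

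**Conclusion.** The point holds as a defect of wording with a practical safety consequence. It should be fixed and is not a reason to stop the study. As written, section 8.1 suspends scheduled HRSD contacts that need no physical presence, partly on symptoms that Appendix A lists as common drug effects, and it conflicts with the adverse-event duties in sections 8.1 and 8.2. Under assumed visits on days 7, 14 and 21 and a full 14-day hold, up to 2 of 3 on-treatment HRSD contacts are lost at their scheduled time, and visit 6 can move to as late as day 35.

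A reader might go further and conclude that both aims are biased. That is possible but not shown. An off-drug visit 6 depends on tablet counts and dosing during a hold, neither of which is documented; longer or interrupted exposure is equally compatible with the text. Section 7.3 might also exclude such women, but it does not define compliance for a delayed visit. Neither the direction nor the size of any bias can be derived.

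**What to change.** 1. In the COVID-19 paragraph of section 8.1, word the hold so that it applies to in-person procedures: phlebotomy, scans and home contacts. State that the HRSD, self-report scales and adverse-event questioning that are already remote stay on their scheduled dates. For visit 6, say whether the ratings keep their date when the scan is delayed.
2. Reconcile section 8.1 with section 1.5 on the trigger (symptoms or contact) and the length (up to 14 days or at least 14 days), and with sections 4.4.1 and 8.2 on mood and adverse-event monitoring.
3. Reconcile sections 5.7 and 6 (whole supply at visit 3) with the dispensing row of Table 1 and its copy in Appendix A.
4. State what happens to dosing during a hold. Which rule applies is for the investigators to settle.
5. Flag any visit 6 done outside the end-of-week-3 timing, and state in section 7.3 how it enters the protocol-compliant analysis.

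The cost is protocol wording and one flag in the data. The remote visits and the staff who run them are already in place.
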